## 7. Research Plan:

The study is a randomized, open-label, comparative effectiveness clinical trial in 180 total patients with GERD or dyspepsia symptoms who will be randomized to either conventional or genotype-supported treatment of GERD and dyspepsia. A total of 120 patients will be enrolled in the UF Health Gastroenterology Clinics in Gainesville, and 60 will be enrolled in a parallel study (under separate IRB protocol) at Nemours Children's Hospital Gastroenterology Clinics in Orlando, FL. Each site will be responsible for overseeing patient care and research at their respective facility. All participants will have symptoms of GERD or related diseases and be candidates for PPI therapy or on PPI therapy with continued symptoms.

We will enroll a total of 180 patients between the UF Health and Nemours sites, which should allow for sufficient power to detect our efficacy endpoint (see power calculation below). We will also collect data from the health records for up to 24 months after enrollment on upper respiratory infection (cold), sore throat, strep throat, bronchitis, pneumonia, ear infection, acute sinusitis (sinus infection), bone fractures, renal function, and gastrointestinal infections for preliminary assessment of the effects of *CYP2C19*-supported PPI dosing on adverse effects. This exploratory arm will provide data to inform power calculations for a larger study focused on preventing PPI-associated adverse events through genotype-supported dosing.

**Inclusion Criteria.** A total of 120 patients with GERD or related symptoms will be enrolled at UF Health. An additional 60 patients will be enrolled at Nemours Children's Hospital Gastroenterology Clinics under a separate IRB protocol. For this protocol, any patient over the age of 17 who presents to GI clinic with GERD or related symptoms and is either 1) being initiated on PPI therapy or 2) continues to have symptoms despite PPI therapy will be considered eligible for the study.

Exclusion Criteria. This study will exclude patients who have had extensive esophageal or gastric surgery or any major chronic illness or condition that in the opinion of the gastroenterologist that would interfere with participation in the study.

Participant Recruitment Methods.

Prior to enrolling their patients, clinicians at participating GI clinics (investigators for this study) will be asked to complete surveys that assess their knowledge, attitudes, and beliefs as they relate to pharmacogenetics testing.

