Patients will be approached for participation at their GI clinic visit by the treating clinician and/or physician assistant. After providing informed consent, patients will be randomly assigned to either conventional treatment or genotype-supported PPI therapy using a randomization table. A 5-ml (one teaspoon) venous blood sample will then be drawn by a nurse, physician assistant, or phlebotomist. The patient will be asked to complete 3 surveys/questionnaires: the Reflux Disease Questionnaire (RDQ), Global Overall Symptom (GOS) scale, and a survey to assess knowledge, attitudes, and beliefs about pharmacogenetic testing. Patients will receive a total of \$25 for participating in this study. The \$25 VISA gift card will be provided after completing the final questionnaire. Patients in the control group may be withdrawn prior to completion if they or their physician elect to order the genetic test during the study. These patients would receive a \$10 VISA gift card for their participation up to the point of withdrawal.

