## **9. Data Safety Monitoring Plan**

Based on assessments of the risk-to benefit ratio, the risk level associated with the study is low. All risks have been described in the consent form.

Monitoring for documentation of an adverse event, whether anticipated or unanticipated, is the responsibility of the principal investigator who will maintain oversight but may delegate collection of information related to this function to other study team members. In term of SAFETY monitoring, all adverse events spontaneously reported, elicited, or observed by the investigators will be recorded. All Serious Adverse Events, should they occur, whether study-related or expected, will be documented on a Case Report Form, under Adverse Event section in the Patient's binder, reported by the principal investigator to the IRB within five (5) working days.

In addition, the principal investigator will follow the reporting requirements for serious and unexpected adverse events outlined in the UF IRB Adverse Event Evaluation and Reporting Guide. All unanticipated, serious, fatal and/or life-threatening adverse events will be reported to

the UF IRB. Aggregate reports of adverse events will be prepared on an annual basis or at the end of the study, whichever may occur earlier and forwarded to the IRB at annual review.

**Plan for data management:** Case Report Form (CRF) within REDCap will be used for each subject. To protect the participant's right of privacy, subjects' individual records related to the study and will be stored in locked cabinets with limited access, and electronic files will be kept in secured database. A de-identified dataset from the database using a patient identification number will then be shared with statistician for analysis. During the study, data will be analyzed as it becomes available by [name] and the investigator team. No early closure is planned because of the limited scope and projected low risk of the study.

There is a prospect of direct benefit to individual subjects, in that genotype information could lead to improved patient outcomes.

Nevertheless, in the absence of a direct benefit, the study may advance the fields by provided an increased understanding of the utility of CYP2C19 genotyping for PPI dosing. Such understanding is deemed essential for broader dissemination of genotyping into clinical care.

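### UF lists the genotype sample and the baseline RDQ after open assignment from a table with no concealment described, and the two parts of the document disagree on the order

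*Combined protocol and SAP*

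**What the plan says.** Section 7 (Research Plan) of the UF protocol describes the design in these words: "The study is a randomized, open-label, comparative effectiveness clinical trial in 180 total patients". Under Participant Recruitment Methods it says who recruits: "Patients will be approached for participation at their GI clinic visit by the treating clinician and/or physician assistant". The same section identifies the participating clinicians as study investigators, and under genotyping and result reporting it leaves the final prescribing decision to the treating physician.

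The allocation method is one sentence: after consent, patients are "randomly assigned to either conventional treatment or genotype-supported PPI therapy using a randomization table". The document does not say who generates or holds the table, whether it is blocked or stratified, or how the next entry is kept from recruiters.

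The next sentence is: "A 5-ml (one teaspoon) venous blood sample will then be drawn by a nurse, physician assistant, or phlebotomist". The RDQ, the GOS and the knowledge survey follow. The same paragraph lets control patients, and only them, be withdrawn if they or their physician order the genetic test.

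The Analysis Plan tests the main hypothesis by linear regression on the RDQ reduction in RM/UM patients. It names no covariates and gives no rule for missing samples.

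The Nemours-focused part of the document, under Study Design, covers 60 children and 120 adults. It also uses a randomization table, but names genotyping before random assignment.

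**The concern.** In an open-label trial with a self-reported outcome, two things protect the comparison at the start: recruiters cannot foresee the next assignment, and everything that defines the analysis set and the baseline is collected before the arm is known. As worded, the UF protocol does not describe the first and puts the second in the wrong order.

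Three things are exposed, to different degrees:

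- **Observed membership of the RM/UM set.** Genotype itself cannot change with arm. Whether a patient is seen to be RM/UM depends on giving a valid sample, and that step follows assignment.
- **The baseline RDQ.** It is self-reported and listed after assignment, so patients may answer it knowing their arm. Any shift in it passes straight into the RDQ reduction.
- **Enrolment.** Consent precedes assignment, so enrolment can depend on arm only if the recruiter can see or predict the next entry. The text is silent on this.

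At stake is a difference between arms that exists before treatment acts and that could be read as a treatment effect. Concealment cannot be restored after enrolment.

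**Working it through.** **1. The plan's own figure.** The power section gives about 30 RM/UM patients per arm, alpha 0.05 and 80% power for a standardized effect of 0.74. Table 1 gives 28% + 5.3% = 33.3% RM/UM, and 0.333 × 90 = 29.97 per arm. Taking alpha as two-sided (not stated), the noncentrality is 0.74 / √(2/30) = 2.87. Power is 80.5% by the t distribution and 81.8% by the normal approximation. The stated figure reproduces; the sample size is not the problem here.

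**2. The two orders side by side.**

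| Step | UF protocol, section 7 | Nemours-focused part, Study Design |
|---|---|---|
| 1 | Consent | Consent |
| 2 | Assignment from table | Genotyping |
| 3 | Blood sample | Assignment from table |
| 4 | Baseline RDQ, GOS, survey | Place in the order not given |

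Both texts cover the UF adults, so they cannot both describe the same visit.

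**3. How a baseline shift reaches the outcome.** RDQ reduction = baseline RDQ − 12-week RDQ. If knowing the arm moves the mean baseline report in one arm by δ, the between-arm difference in reduction moves by δ with no treatment effect at all.

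**4. False-positive rate under an assumed bias.** The documents give no bias figure, so 0.1 to 0.3 SD is assumed. For a bias of b SD with n per arm, the test statistic shifts by s = b / √(2/n). The rejection rate of a two-sided 5% test is then 1 − Φ(1.96 − s) + Φ(−1.96 − s).

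UF enrols 120 of 180, so a bias confined to UF is diluted in the pooled sample to b × 120/180. UF alone has 60 per arm, of whom 0.333 × 60 = 19.98, about 20, are RM/UM.

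| Bias at UF | Pooled: diluted bias, s (n = 30) | Pooled rate | UF alone: s (n = 20) | UF rate |
|---|---|---|---|---|
| 0.1 SD | 0.067, 0.26 | 5.8% | 0.32 | 6.2% |
| 0.2 SD | 0.133, 0.52 | 8.1% | 0.63 | 9.7% |
| 0.3 SD | 0.200, 0.77 | 12.1% | 0.95 | 15.8% |

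Using the t distribution instead lowers these by at most about half a percentage point (8.0% and 9.5% in the 0.2 SD row).

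**5. Loss of samples (assumed rate).** If 10% of UF control patients gave no sample, 0.10 × 20 = 2 RM/UM patients would be missing. With 30 against 28, power for an effect of 0.74 is 79.0% instead of 80.5%, which is negligible. Loss matters only if it is selective. If those 2 of 30 differed by 1 SD from those retained, the pooled control mean would move by 2/30 × 1 = 0.067 SD, which gives a false-positive rate of about 6% (first row of the table).

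**The case against.** The strongest objection is that silence is not a defect. The protocol does not say that the table lies in the clinic or that recruiters can read it, and consent comes before assignment. The Nemours-focused part has providers notify a study coordinator of eligible patients, which suggests someone between recruiter and procedures. This stands to the following extent: a reader might infer that recruiters can see the next arm and steer patients, and the documents do not support that. They support only that no safeguard is described. The listing of sample and baseline questionnaires after assignment does not rest on silence; it is written in section 7.

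A reader might also infer that control patients will refuse the sample because their result is held back for 12 weeks. That is conjecture. Both arms are to be sampled, controls do receive their result, and payment follows the final questionnaire. Because genotype is fixed, a later sample could still classify a patient. The arm-specific loss that the document does provide for is the control-only withdrawal rule.

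A reader might apply a 0.2 SD bias to all 180 patients and obtain about 12% for the RM/UM test, or 27% for a comparison of whole arms of 90. The first treats a UF problem as if it affected Nemours equally. The second also concerns a comparison other than the one the main hypothesis names.

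Finally, subtracting baseline removes differences in symptom level, and the regression could take covariates. That is fair, so it would be wrong to say that analysis can do nothing. But no covariates are named, a baseline reported with the arm known is itself the thing in doubt, and selection on unmeasured prognosis would remain.

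**Conclusion.** The point holds in limited form. As written, section 7 of the UF protocol takes the sample that defines the analysis set, and the baseline that enters the outcome, after open assignment, and it describes no concealment of the table. It also conflicts on order with the Nemours-focused study design for the same adults. Observed RM/UM membership and the self-reported baseline can be affected by knowledge of the arm. Enrolment can be affected only if the next entry is foreseeable, which the documents leave open.

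The size is illustrative. A bias of 0.2 SD confined to UF gives about 8% false positives in the pooled RM/UM test and about 10% in UF alone, against 5% nominal; at 0.1 SD the rates are about 6% in both. A 10% loss of UF control samples removes about 2 RM/UM patients. The bias and loss rates are assumptions, and the documents do not show that either will occur. The case for change is that protection is nearly free if put in place before enrolment.

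**What to change.** In section 7, Participant Recruitment Methods, state the order as consent, blood sample, baseline RDQ, GOS and survey, then assignment. At UF the genotype takes about 2 weeks, so sampling first reveals nothing before assignment. That argument is specific to UF, since Nemours describes a platform with a turnaround of about one hour.

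Replace the table by a computer-generated schedule in random-size blocks, held away from those who recruit, with each assignment released only after the patient is registered. REDCap is a natural vehicle, since the data management plan states "Case Report Form (CRF) within REDCap will be used for each subject". The document records it for case report forms only, so its use for assignment would need to be confirmed.

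Reconcile the Study Design text in the Nemours-focused part with this order for the adults, and apply the same concealment to the table named there.

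The cost is setting up one schedule and reordering steps within a single visit. Sample size, visits and eligibility do not change.

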#### **4. Background:**

In the past 10 years, there have been significant advances in defining genetic determinants of drug response. These advances have led to the expectation by many that eventually an individual's personal genetic information will become part of his or her medical record to be used to guide treatment decisions. The UF Health Personalized Medicine Program (PMP) was created at UF to meet this expectation. The initial efforts of the PMP involved implementation of cytochrome P450 (CYP) 2C19 genotyping to guide antiplatelet therapy following percutaneous coronary intervention.

At UF Health, *CYP2C19* genotyping is available clinically. However, the gastroenterologists do not use *CYP2C19* genotype information, and there is a need for further evidence generation, which propose to do through a pilot implementation study. The proposed study is significant because it may extend the evidence regarding influence of *CYP2C19* genotype in PPI efficacy, lead to more rationale dosing of PPIs and management of patients with GERD or dyspepsia, and build a body of evidence to facilitate the implementation of pharmacogenetic-supported GERD and dyspepsia management.

**GERD Refractory to PPI Treatment.** Gastroesophageal reflux disease (GERD) affects 10-20% of individuals in Western countries. PPIs are agents of choice to treat GERD, and are among the highest-selling classes of drugs in the US, with \$9.5 billion in sales in 2015. Six PPIs are commercially available: omeprazole (Prilosec); lansoprazole (Prevacid), dexlansoprazole (Dexilant) esomeprazole (Nexium), pantoprazole (Protonix), and rabeprazole (Aciphex). Low doses of omeprazole and lansoprazole can be purchased over the counter. While effective for symptom relief and erosive esophagitis, PPI treatment fails in up to 40% of patients with GERD. Failure to respond to standard, once daily PPI treatment or complete or partial response to twice daily PPI treatment has been defined as refractory GERD. Several factors have been associated with refractory GERD, including adherence to PPI therapy, esophageal hypersensitivity and inter-individual differences in PPI metabolism^11.

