Genotyping and result reporting. Genotyping will be done by the CLIA-licensed UF Pathology Laboratory, as has been done for over 1,600 patients in the UF Health CYP2C19-clopidogrel implementation, with genotype results reported in the EHR. For patients randomized to the genotype-supported arm, genotype results will be available in approximately 2 weeks. For patients randomized to the conventional treatment arm, the genotype results will be resulted in the EHR after the patient completes study participation (12 weeks after patient enrollment). The patient's clinician will be educated about the genotype results and their implication for PPI response. A recommendation for a dose increase will be provided for RMs and UMs (approximately 30% to 35% of patients). For patients with other genotypes, clinicians will be advised that usual PPI doses are expected to be effective that lower doses may be sufficient for symptoms management in PMs. Clinicians will also be provided quick reference guides that will include phenotype, genotype, dosing recommendations, and educational information. The PMP Committee has convened with the GI clinicians to evaluate and approve the dosing recommendations for adults based on CYP2C19 genotype. Clinical decision support tools in the EMR will also be implemented that will provide this guidance to the treating clinician. While dosing recommendations will be provided based on genotype results, the ultimate prescribing decision will be left to the discretion of the treating physician.

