Assessment of PPI efficacy and adverse effects. Our primary outcome will be the effectiveness of PPI therapy, which will be determined via two questionnaires: RDQ and GOS scale, administered by study personnel at baseline and 12 weeks. The RDQ was developed to monitor treatment response over time and evaluates 6 symptoms (12 items) covering 3 domains: heartburn, regurgitation, and upper abdominal pain. Each symptom is evaluated using a 6-point Likert scale to assess frequency and severity over the previous week. Each symptom is rated from 1 (did not have) to 6 (severe), and the RDQ mean score is calculated as the mean response to the 12 items. The RDQ mean score thus ranges from 1 to 6 and has been psychometrically validated. The GOS scale evaluates 18 symptoms, with each rated from 1 (no problem) to 7 (very severe). Similar to the RDQ, the mean score is calculated as the mean response to the 18 items, with mean scores ranging from 1 to 7. Patient participation will end after they complete the approximate 12 week questionnaire. However, we will continue to

follow patients over 24 months through medical record review to assess adverse outcomes for occurrence of upper respiratory infection (cold), sore throat, strep throat, bronchitis, pneumonia, ear infection, acute sinusitis (sinus infection), bone fractures, renal function and gastrointestinal infections.

Metrics for assessing success of pharmacogenetic testing in clinical practice. We will test a variety of variables that will provide insight into attitudes and acceptability of pharmacogenetic testing. These will include: 1) percent of patients approached about the study who agree to participate; 2) surveys of patients and clinic staff on knowledge, attitudes, and beliefs about pharmacogenetic testing; and 3) the percent of the time a dosing recommendation for a patient in the genotype-supported arm is accepted by the clinician. Patients will be surveyed about knowledge, attitudes, and beliefs about pharmacogenetic testing using questionnaires on enrollment and at the end of their study participation. Clinic staff will be surveyed about knowledge, attitudes, and beliefs about testing at the beginning and end of the study.

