### **Analysis Plan and Power Calculations:**

We will test the hypothesis that RMs/UMs (1 or 2 gain-of-function alleles) in the genotype-supported arm have better GERD and symptom control than RMs/UMs in the conventional treatment group because they will have their dose increased based on their genotype.

Continuous variables will be compared between the genotype-supported group and the conventional treatment group using the Student's unpaired *t*-test, and categorical variables will be compared using the chi-square or Fisher's exact test. The hypotheses will be tested using linear regression analysis to estimate the difference in the RDQ reduction in the RM/UM patients between the two arms. All analysis will be performed in SAS 9.4 (Cary, NC).

We will evaluate the percentage of the time when a dosing recommendation was made and accepted by the treating clinician, to provide practical data on the willingness of clinicians to adopt this approach. We will also collect patient- and provider-level survey data on knowledge, attitudes, and beliefs about pharmacogenetics testing, using survey tools adapted from other IRB-approved studies.

Power calculation. While there are no data in the literature on genotype associations with the efficacy endpoint we will use (symptom improvement), there are pH probe data by genotype that were generated by the Nemours investigators, that we can use, and this should be an excellent surrogate for symptom data. We have done power calculations based on two of the pH-based response phenotypes, found in Table 3. Specifically we powered based on percent time with pH < 4 (which has an effect size of 0.79) and acid clearance time (effect size of

0.45). Based on these two phenotypes, we have the following power to detect differences in efficacy between *CYP2C19\*17* carriers and non-carriers:

Based on the previous data for acid clearance time, with 180 total participants (120 from UF Health and 60 from Nemours), we have 81% power to detect a 0.49 effect size.

Based on the previous data for time with pH <4.0, with 180 participants, we have >99% power to detect a 0.79 effect size.

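### Adult protocol: withdrawing only those control patients for whom the genetic test is ordered, before the 12-week RDQ and GOS, may bias the RM/UM comparison; keep them and analyse as randomised

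*Combined protocol and SAP*

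**What the plan says.** The rule stands in the adult (UF Health) protocol, section 7, under Participant Recruitment Methods: "Patients in the control group may be withdrawn prior to completion if they or their physician elect to order the genetic test during the study". It applies to the conventional arm only. A withdrawn control receives a $10 "VISA gift card for their participation up to the point of withdrawal"; a patient who completes the final questionnaire receives $25.

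Under Assessment of PPI efficacy and adverse effects, the primary outcome comes from the "RDQ and GOS scale, administered by study personnel at baseline and 12 weeks". There is no assessment in between. The same paragraph says that patient participation ends with the 12-week questionnaire, and then that the study will "follow patients over 24 months through medical record review to assess adverse outcomes". It does not say whether this covers withdrawn patients.

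The Analysis Plan uses "linear regression analysis to estimate the difference in the RDQ reduction in the RM/UM patients between the two arms". It names no analysis set and gives no rule for patients without a 12-week score.

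On how often the test might be ordered, Background says that at UF Health "genotyping is available clinically. However, the gastroenterologists do not use *CYP2C19* genotype information". The laboratory already runs the assay, "as has been done for over 1,600 patients in the UF Health CYP2C19-clopidogrel implementation". For controls, "the genotype results will be resulted in the EHR after the patient completes study participation", that is, 12 weeks after enrolment.

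The paediatric (Nemours) text, as available, has no comparable rule. Its stipend paragraph speaks only of participants who themselves decide to leave.

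**The concern.** The rule removes randomised patients from one arm because of something that they or their unblinded physician choose after randomisation. Eligibility includes patients who still have symptoms on a PPI, so a link between poor response and ordering the test is plausible. If such a link exists, the controls with a 12-week score are no longer comparable with the genotype-supported arm.

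The direction is open:
- If poor responders order, the remaining controls look better and a benefit is partly hidden.
- If good responders order, the benefit is exaggerated.
- If ordering has nothing to do with reflux symptoms, for instance because the test is wanted for clopidogrel, there is no bias and only a small loss of numbers.

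**Working it through.** **Inputs from the adult protocol.** 180 patients, 90 per arm; about 30 RM/UM per arm; alpha 0.05; 80% power for an effect of 0.74 SD; 120 adults and 60 children.

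**The plan's own figure.** Two-sided two-sample t-test, 30 v 30: noncentrality = 0.74 × √(30×30/60) = 2.87 on 58 df, power 80.5%. The stated 80% reproduces, provided that all 30 per arm have a 12-week score.

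**Assumptions, not in the documents.** Equal allocation among adults gives 60 adult controls, and one third of these, 20, are RM/UM; the other 10 are children. The outcome is normal with SD 1. The k adult RM/UM controls with the highest propensity to order leave, with k = 1, 2 or 4. That is 5%, 10% or 20% of the 20, or about 3, 6 or 12 of the 60 adult controls if ordering is unrelated to genotype. Propensity has correlation r with a worse outcome.

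**Apparent effect after withdrawal.** The expected sum of the top k of 20 standard normal values, divided by (30 − k), is 0.064, 0.117 or 0.205. The apparent effect is 0.74 − r × this shift. For r = 0.5 and k = 4: 0.74 − 0.5 × 0.205 = 0.64 SD.

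**Total false-positive rate with no true effect.** By simulation, two-sided t-test.

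| r | Apparent effect, SD (k = 1/2/4) | False positives, % (k = 1/2/4) |
|---|---|---|
| 0.5 | 0.71 / 0.68 / 0.64 | 5.3 / 5.6 / 6.8 |
| 0.25 | 0.72 / 0.71 / 0.69 | 5.1 / 5.2 / 5.5 |
| 0 | 0.74 / 0.74 / 0.74 | about 5 |
| −0.5 | 0.77 / 0.80 / 0.84 | 5.3 / 5.6 / 7.0 |

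At r = −0.5, false positives favouring the genotype arm alone rise from 2.5% to about 3.4%, 4.1% or 6.1%. If the patients are kept and their scores obtained, the total stays at about 5% throughout.

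**Cost of keeping them.** The upper bound assumes that each kept patient gains the full 0.74 SD from the test. Dilution is 0.74k/30 = 0.02, 0.05 or 0.10 SD pooled, and 0.74k/20 = 0.04, 0.07 or 0.15 SD in adults alone.

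**Power in adults alone.** The paediatric assessment section lists no RDQ, so 20 v 20 may be the relevant comparison. Power with no withdrawals is then about 63%.

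| r | Kept, % (k = 1/2/4) | Withdrawn, % (k = 1/2/4) |
|---|---|---|
| 0.5 | 59 / 55 / 47 | 56 / 51 / 40 |
| 0.25 | 58 / 54 / 45 | 59 / 55 / 48 |
| 0 | 57 / 53 / 43 | 61 / 60 / 58 |

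Simulation error in the power figures is about 1 point.

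**The case against.** **Orders may be few.** The gastroenterologists do not currently use the genotype, the participating clinicians are themselves study investigators, and controls receive their result after 12 weeks anyway. This stands, although it describes practice before a trial that educates clinicians about the genotype. It limits the likely size; it does not remove the flaw.

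**The rule is permissive and has a purpose.** A control who is tested early no longer receives untested care, and limiting contamination is an understandable aim in a pilot. That stands as a reason to want such a comparison. But discretion without criteria adds a second post-randomisation choice, and the aim can be met by a sensitivity analysis.

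**Keeping the patients dilutes the effect.** True. Pooled, the kept estimate is at worst 0.74 × (1 − k/30) = 0.72, 0.69 or 0.64 SD, no nearer to 0.74 than the withdrawn estimate at r = 0.25. In adults alone, power is equal or lower when they are kept at r = 0.25 and clearly lower at r = 0.

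**Stronger readings.** A reader might infer that the rule breaks the randomised comparison. The figures do not support that: one leaver at r = 0.5 gives about 5.3% error, and four at r = 0.25 about 5.5%. A reader might also infer that the rule is known to hide, or to inflate, a benefit; the documents fix no direction. Nor do they show that adverse-event record review stops for withdrawn patients, or that it continues.

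**Conclusion.** The concern holds as a possible bias of unknown size and direction. The rule acts in one arm only, is triggered by choice after randomisation, and falls before the only post-baseline symptom scores. That these patients give no 12-week score is the natural reading rather than an explicit statement, but nothing in the plan repairs the gap.

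The figures are illustrations. They rest on assumed losses of 5% to 20% of adult RM/UM controls and assumed correlations. Within that range the effect on the false-positive rate runs from none to about 2 points pooled. The argument for change is validity: a comparison as randomised, with scores obtained, keeps its error rate whatever drives ordering. This is a cheap improvement, not a fatal defect.

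**What to change.** Replace the withdrawal sentence in the adult protocol so that a control patient for whom the test is ordered stays in the study, completes the 12-week RDQ and GOS, receives the full $25, and is analysed in the conventional arm as randomised. State this analysis set in the Analysis Plan. Record the dates of order and result, and report the counts by arm. Add one sensitivity analysis excluding these patients, which preserves the contamination-free comparison. State whether the 24-month record review includes anyone who is withdrawn.

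Blood is drawn at enrolment in both arms, so kept controls can still be classed as RM/UM. Whether to order the test remains a clinical decision.

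The cost is a short protocol change (and the consent form if it repeats the rule), one questionnaire and $25 − $10 = $15 per affected patient, and the dilution shown above. The change should not be presented as a gain in power.
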